#### **10.1.4 Classification of adverse reactions regarding the study drug**

*The clinical investigator will perform an evaluation of the adverse events after the verification of all accessible data and, if required, he/she will reevaluate the case when new information become available. The investigational products include the test drug under evaluation and the reference drug, that are given during any period of the study.*

*The investigator will judge, whether warranted or not, in his/her opinion, if the adverse event is related to the drug according to the following classification:*

*The investigator should report the evolution of the clinical outcome, considering the following evolution:*

- Recovered;
- Not Recovered;
- In recovery;
- Recovered with sequel;
- Worsening;
- Death.

#### **10.2. PPD / Emergency procedures**

PPD

PPD

**10.2.1 Procedures during the study**

*During confinement, in each study period, the participants will be followed by the healthcare professionals during all the period viewing the detection of adverse events, including signs of toxicity.*

*The participants will be instructed about the potential adverse events, as well as the need to inform them immediately to the investigator or his/her team.*

*Each participant will be requested to report any adverse event symptoms and it has occurred. The medical team will also be requested to notify the principal investigator if the use of additional medication has been required. Any adverse event occurring during the study period will be recorded according to item 10.3.*

*The questions performed to know if the participant has had some adverse event must be limited to general questions, such as: How are you?*

*Any adverse events occurring after hospitalization must be immediately informed to the team by any mean (telephone, personally, e-mail, etc.).*

*Upon blood collections, heart rate, blood pressure, and body temperature will be measured (according to Table 2).*

*Although there is no ICU in this unit, a mobile ICU will be on the alert during the performance of the study and an intensive care physician will be present to provide first aid. In case of the Levothyroxine Sodium the mobile ICU will be parked at PPD available for the participants for 10 hours after the administration of the drug. PPD*

*PPD will be qualified to perform emergency care and subsequent transfer to PPD which is located*

*PPD has the infrastructure to help and provide care to the usual complications whether se events of the drug mentioned. It also has a structure for first aid and an intensive care physician available.*

PPD

**10.2.2 Post-study procedures**

*Upon discharge of the last hospitalization, all the participants will be warned once again that they must not donate blood or take part in any clinical trial with drugs, involving the collection of blood, for at least 6 months.*

*All the participants, including those who have withdrawn or have been excluded from the study after the administration of at least one dose of one of the drugs, must be clinically reevaluated (including vital signs, physical examination, and ECG) and have subsidiary lab tests similar to those performed on pre-study (except for serologica, and feces tests).*

*The participant who present altered results in the post-study examinations or any adverse event related to the study should be accompanied to the parameters return to normal or until the doctor feels irrelevant changes.*

*Regardless of the change, all the results obtained must be reported in the participant's case report form.*

*The negative or non attendance of the participant to perform these procedures, must be duly documented.*

PPD

*All adverse reactions occurred in the period between the signing of the Informed consent form until the time of completion of the clinical phase of the study, or until the issuance of test results post-study (or at the discretion of the clinical investigator) will be registered in the Non-Serious Adverse Event Notification Form (RQ-017) as in Annex 4, or whether the reaction is not related to study medication, and for the events considered as serious, they will be registered in Serious Adverse Event Form (RQ-018) as in Annex 5 and will be registered in the Clinical Report up to the date of its finalization.*

*The participant who has any adverse reaction (laboratory or clinical) will be followed until the reaction disappears.*

*The medical/disease conditions present before the beginning of the study will only be considered as adverse events if their status is aggravated after the participant inclusion. Abnormal laboratory values or test results constitute EA only if induce clinical signs or symptoms if they are clinically relevant or if they require treatment.*

*Once an AE is detected, it must be followed until its resolution or until it is considered permanent, and the evaluation must be performed at each visit (or more frequently, if required) to evaluate any change in severity, suspected relation with the investigational drug, the interventions required to treat them, and the results.*

PPD

**10.4 Notification of serious adverse event**

*Any adverse reactions or abnormal values of laboratory tests that are classified as serious occurring during the study will be reported immediately to the principal investigator, the sponsor of the study, the Ethics Committee (CEP) and ANVISA [CETER (Coordination of Therapeutic Equivalence) - and Pharmacovigilance Management] within 24 hours. Recurrent episodes, complications, or progression of EAG initial monitoring shall be reported as the original episode, regardless of when the event occurs. Any experienced SAEs after the final visit of the volunteer and for the duration of life insurance should also be notified if the investigator suspects a causal relationship with the drug under investigation.*

PPD

### 10.5 Pregnancy

If pregnancy occurs after signing the consent form until the end of the study (completion of post-study studies) it should be reported to the Ethics Committee and registered with the Notification Form and Pregnancy Monitoring (RQ - 412), according to Annex 8. The PPD will route the participant to search for prenatal and PPD team will be following all the prenatal period until the baby birth.

For the research participants who eventually became pregnant (directly or indirectly) after the signing of the informed consent, a quarterly gestational follow-up will be required, as described below:

- End of 1st quarter: preferably between the 12th and 16th weeks;
- End of 2nd quarter: preferably between 24th and 28th weeks;
- End of 3rd quarter: preferably between 36th and 40th weeks;
- Postpartum: preferably 15 to 20 days after child-bearing;
- In the first 6th month of the child's life;
- In the first year of the child's life.

All efforts should be made for postpartum follow-up and child development up to 1 year of age so that we can assess their psychomotor development.

Any SAE experience during pregnancy must be recorded in the SAE Notification Form.

PPD

### 10.6 Life Insurance

For a period of 120 days, from the date of the 1st hospitalization, the participants will be covered by a life insurance, regarding eventual adverse events that might arise from the administration of the drug, and in cases of death and permanent disability, related or not to the clinical trial.

PPD

## 11

PPD

### 11.1 Basic principles

The study will be conducted according to the current version of the ICH/GCP – Guideline (CPMP/ICH/135/95) and according to the Declaration of Helsinki (1964) and its reviews of Tokyo (1975), Venice (1983), Hong Kong (1989), West Somerset (1996), Edinburgh (2000), Washington (2002), Tokyo (2004), and Seoul (2008) and Fortaleza (2013), as well as local regulations (Resolution 466/12 and 251/97 of the Brazilian National Board of Health - Ministry of Health, as well as Resolution RDC 016/07 by ANVISA).

The investigators are responsible for conducting the study in strict compliance to the approved protocol.

PPD

### **11.2 Ethics Committee (EC)**

*This protocol and the informed consent form will be submitted to the Ethics Committee registered on the Brazilian National Research Ethics Committee (CONEP) of CNS/MS for appraisal. The study will be conducted according to the Brazilian National Health Board - Ministry of Health (CNS-MS) Resolution 466/12. The study mentioned will only be started after the evaluation and approval of the Ethics Committee. All the corrections to this protocol must be approved by the Ethics Committee before applied, unless both in the investigator's and the physician's opinion, such delay would jeopardize the participant's health or life. If this risk is considered imminent, the investigator and the participant's physician may take all the actions considered of the best interest to the participant.*

*The Ethics Committee will have access, via Platform Brazil the curriculum of the researcher and the research project (Research Report) previously registered, the cover sheet signed and the Informed Consent Form. The sponsor and the Ethics Committee must be notified when and why such deviations from the protocol were required.*

*At the end of the research the PPD will submit to the EC a copy of the Final Report.*

PPD

PPD

### 11.3 Informed Consent Form

The participants will receive an explanation of the nature and objectives of the study. It will be emphasized that the study is a research, and that the participant cannot wait that there is any therapeutic effect. The participant will also understand that he is free to withdraw from the study at any moment, with no obligation to provide the reason to do it and without any harm to he/she care at PPD

The participation of the participants in the recruitment and screening activities will be followed by previous authorization according to the Recruitment Form. Once the participant's participation in the study is approved after an appropriate time for deliberation, each participant will be requested, if they agree, to sign the Informed Consent Form (Annex 3) to participate in the study, before hospitalization in the first period of treatment. It is a responsibility of the Clinical Investigator to obtain the signature of the Informed Consent Form. If the clinical investigator's responsibility to obtain the PPD is designated to another team member, this designation must occur upon a proper instrument between the parties.

at the Investigator in Charge opinion, a Protocol amendment changes substantially the study design or the risk the participants will be submitted to, the participants will be informed, and must sign a new consent regarding the decision to continue to participate in the study.

The informed consent form must comprise the changes and/or amendments, if any, presenting in its text only duly amended final information, in order not to confuse the participant.

PPD

### 11.4 Reimbursement

The participants will be reimbursed in the amount of R\$ 870.00 (Eight hundred and seventy reais) regarding the expenses and time taken during the study.

It is important to highlight that, as this is a reimbursement for the time taken and incurred expenses, in case of withdrawal of the participant or absent in collections extras, this reimbursement will be proportional to the period the participant has participated in the study. The participant's participation in the screening process, regardless the approval or agreement to participate, will not be reimbursed.

PPD

PPD

**11.5. Confidentiality**

*The records that could identify the participant will be kept confidential. However, lead researcher and team members will have access to original records of clinical participant data, to the extent permitted by law and regulations, in order to verify the procedures and test data, without violating the condition that information can't be disclosed. Auditors, the study sponsor and members of the Research Ethics Committee only have access to test results and medical history of the participants, but not to personal data. By signing the consent form Clarified, the participant is authorizing such access, even to give up the study.*

**12**

PPD

**/ Analytical methods**

PPD

**12.1 Description**

*The analytical methodology that will be used to determine the drug (Levothyroxine T4) in the plasma of the volunteers will be the high performance liquid chromatography (HPLC) using mass spectrometer (MS).*

PPD

PPD

### **12.2 Validation of the analytical procedure**

The validation of the analytical method is performed according to the Guide for Validation of Bioanalytical and Analytical Methods (RDC Resolution nº 27, dated 17/05/2012), through experimental studies that the method meets the requirements of analytical applications, ensuring the reliability of the results. Thus, the method should provide precision, accuracy, linearity, residual effect, matrix effect, selectivity, reproducibility, stability, according to the specifications of each test.

Thus, the equipment and materials must be properly calibrated, analysts must be skilled and trained and chemicals pharmacopoeia or properly characterized reference.

The following validation tests are performed:

- Selectivity;
- Residual effect;
- Matrix Effect;
- Calibration curve;
- Precision;
- Accuracy;
- Recovery.

To test the stability of the drug in biological fluid the following tests shall be performed in accordance with Resolution - RDC nº 27 of 17/05/2012:

- Stability after freezing and thawing;
- Short term stability;
- Long term stability;
- Post-processing stability.

It should also be tested for drug stability in solution for a period and storage conditions:

- Stability of analyte and internal standard solution.

PPD

PPD

### 13 Data analysis / Statistical methods

*The statistical phase of this study includes the choice of an experimental design adequate to the intra subject variability of the analyte in question (or its inter variability, if it is the case) and the adequate sample size determination.*

*The statistical methodology foresees the construction of at least two confidence intervals (CI\_90%) for the ratio of the geometric means of the reference and test (1 and 2) treatments for the primary parameters (T/R), and a significance analysis of the fixed effects, adequate to the experimental design, through the application of the Variance Analysis technique (ANOVA). This last analysis aims exclusively to identify which factors would have greater influence in the answer, in case it had not been isolated as being a source of variation.*

*In this study it will be included the data of all participant who finished all the periods of the study. The points outlining the Plasma Concentration versus Time curve will only be reanalyzed if there is an analytical reason for doing so.*

*The Variance Analysis (ANOVA) model will include the terms sequence, formulation and period as fixed effects, and subject nested within sequence as a random effect. The sequence effect will be tested using the term subject nested within sequence as a term of the error with the level of significance of 10%.*

*The estimation to be obtained for the experimental error will be used in the construction of the confidence intervals for the final conclusion.*

PPD

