
PPD / Dose
	
PPD
 
600mcg of Levothyroxine Sodium equivalent to 3 tablets of the test drug or 3 tablets of the comparator drug.

PPD / Collection Time
	
PPD
 
In each study period will be collected blood in the following times : (-) 00:30 (baseline); (-) 00:15 (baseline); 00:00 (5 minutes before dosing); 0:30; 01:00; 01:30; 02:00; 02:30; 03:00; 03:15; 03:30; 03:45; 04:00; 04:15; 04:30; 04:45; 05:00; 05:30; 06:00; 06:30; 08:00; 10:00; 12:00; 24:00; 36:00; 48:00 and 72 hours after the administration of the medication.

PPD / Confinement period
	
PPD
 
24 hours.

PPD / Safety procedures
	
PPD
 
Monitoring clinical tolerability (adverse events, laboratory parameters), pregnancy test (urinary) for women before each study period, vital signs (blood pressure, temperature and heart rate ), ECG, total and free T3 and T4, and TSH.

PPD / Post study procedures
	
PPD
 
Laboratory examinations (hematological, biochemical, urinalysis) adverse events monitoring and ECG.        B-HCG for women after the last blood collection of the last period.

PPD / Analytical Methodology
	
PPD
 
Determination of Levothyroxine (T4) by techniques of liquid chromatography coupled to tandem mass spectrometry (LC MS/MS).

PPD / Pharmacokinetic
	
PPD
 
Primary: <math>C_{max,adj}</math>; <math>AUC_{0-72,adj}</math>        Secondary: <math>T_{max}</math>, <math>AUC_{0-72}</math> and <math>C_{max}</math>.

PPD Baseline adjusted
	
PPD
 
Difference between each point of the plasma concentration curve of each research participant/period and the mean of the basal levels (3 points). Neaative values will be automaticallv replaced with zero.

PPD / Statistical Analysis
	
PPD
 
The calculated 90% confidence interval of the ratio of plasma levothyroxine (T4) concentration, calculated from the geometric means of the Ln transformed values, should fall between 80% - 125% for <math>C_{max,adj}</math> and <math>AUC_{0-72,adj}</math>.

PPD / Adverse events
	
PPD
 
The observed or mentioned (via nonspecific questions) adverse events will be documented, analysed and reported according to their severity and causality.

PPD
 
/ Data analysis plan
	
PPD
 
Descriptive statistics, relative bioavailability estimation, construction of confidence intervals (parametric and non-parametric), application of an ANOVA.

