### **6.7 Criteria for the discontinuation or withdrawal of participants from the study**

The following criteria will be considered for the discontinuation of withdrawal of research participant from the study:

1. *Withdrawal of the subject's consent;*
2. *Occurrence of pregnancy;*
3. *Occurrence of adverse events leading the research participant to drop out of the study, such as unavailability or intolerance to the study procedures;*
4. *Adverse effects of the drug mentioned that are considered clinically significant by the physician in charge and/or harmful to the research participant's health;*
5. *Abnormal lab tests considered as clinical relevant;*
6. *Intercurrent diseases requiring medication;*
7. *Unfulfillment of the established rules;*
8. *Research participant present during the pre-admission (Period 1 or 2) tested positive for alcohol and/or drug test;*
9. *Research participant (for the women) present during the pre-admission tested positive for pregnancy test;*
10. *Chew the tablet during drug administration;*
11. *Study interruption;*
12. *Need to use some prohibited medication during the participation in the study;*
13. *To find out that the research participant does not meet the study requirements;*
14. *If the research participant take during the study any medication which contains the same substance which will be used as internal standard during the analysis of the plasma samples;*
15. *Research participant did not ingest the entire dose of the study drugs provided;*
16. *Research participant losing the last point of collection of the periods (period 1 or 2);*

17. All cases where the principal investigator considers failure to the protocol and can make questionable the result of the study (severe adverse reaction or serious event adverse, Indiscipline of the subject, failure diet);
18. Unlikely to comply with the protocol requirements, instructions and trial-related restrictions; e.g., uncooperative attitude, inability to return for visits, and improbability of completing the trial;
19. In case of vomiting or diarrhea episodes after the administration of the drug until two times the Tmax of the active ingredient and/or metabolite, regarding the pharmaco mentioned, Levothyroxine, research participants having episode of vomiting or diarrhea within 08 hours after the administration must be excluded.

PPD

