**13.6 Safety Analysis**

*Not applicable.*

PPD

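### Section 13.6 sets no safety analysis although the synopsis promises that adverse events will be analysed, and no all-dosed analysis set is defined

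*Combined protocol and SAP*

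**What the plan says.** The synopsis entry on adverse events says that "adverse events will be documented, analysed and reported according to their severity and causality". Its safety-procedures entry lists adverse events, laboratory parameters, vital signs, ECG, thyroid hormones and TSH.

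The statistical chapter does not carry this through:

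- Section 13.6, Safety Analysis, consists of "Not applicable". Section 13.5, on other endpoints, says the same.
- The only inclusion rule, in the opening of Section 13, is that "it will be included the data of all participant who finished all the periods of the study".
- The synopsis data analysis plan names "Descriptive statistics, relative bioavailability estimation, construction of confidence intervals (parametric and non-parametric), application of an ANOVA". The contents listed for the statistical report, ahead of Section 13.3.1, are concentration tables, pharmacokinetic parameters and mean curves.

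Section 6.7 provides for withdrawal on safety grounds, including "Occurrence of adverse events leading the research participant to drop out of the study" and "Adverse effects of the drug mentioned that are considered clinically significant by the physician in charge". Section 10.2.2 requires post-study re-evaluation of all participants, "including those who have withdrawn or have been excluded from the study after the administration of at least one dose". The documentation text that follows it puts events on forms RQ-017 (non-serious) and RQ-018 (serious), and they "will be registered in the Clinical Report up to the date of its finalization".

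**The concern.** The synopsis and Section 13.6 cannot both be followed. One commits the trial to analysing adverse events; the other says there is no such analysis. Sections 13 to 13.5 and the synopsis data analysis plan do not fill the gap.

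The population rule adds a second problem. It is not worded as applying to pharmacokinetics only, and it sits in the general opening of the statistical chapter. Several withdrawal criteria in Section 6.7 are themselves safety outcomes. One removes a participant for vomiting or diarrhoea within 8 hours of dosing, and Section 1.3.5 lists both as reactions to levothyroxine. Membership of the completer set can therefore depend on tolerability, which makes it unsuitable as a default denominator for safety.

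What is at stake is descriptive: whether the report will say how many of those dosed with the new formulation had events, and how many of those dosed with the comparator, each participant having been given 600 mcg.

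**Working it through.** This is mainly a comparison of texts, with one small piece of arithmetic.

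**Step 1. Commitment against plan.** The synopsis uses three verbs: document, analyse, report.

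| Task | Where the documents provide for it |
|---|---|
| Document | Section 10.2.2 and the documentation text after it; forms RQ-017 and RQ-018 |
| Classify by intensity and causality | Sections 10.1.3 and 10.1.4, Table 3 |
| Report | Entry in the Clinical Report; serious events under Section 10.4 |
| Analyse (counts, denominator, split by formulation) | Nowhere; Section 13.6 rules it out |

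Only the analysis step is missing.

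**Step 2. Scope of the completer rule.** The sentence follows the paragraph on confidence intervals and ANOVA. The next sentence in the same paragraph concerns reanalysis of concentration-time points, and the ANOVA model comes after that. The likely intent is the pharmacokinetic set. On that reading safety has no analysis set at all; on the literal reading its set would be completers. Neither gives an all-dosed denominator.

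**Step 3. Can the tables be built from planned data?** RQ-017 records period, treatment code, onset relative to dosing, intensity and causal relationship. RQ-018 records period, treatment code, date of last administration and causal relationship. RQ-018 as annexed has no intensity box, so intensity for serious events must come from the investigator's grading under Section 10.1.3. Dosing records give the denominators. No new data collection is needed.

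ECG and laboratory tests, including thyroid tests, are scheduled before and after the study, not between periods (chronogram). Under Section 10.2.2 the post-study results go into the case report form. For a completer the change from pre-study to post-study spans both formulations and cannot be split between them.

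**Step 4. Size.** Inputs from Section 13.1: 60 evaluable, 20% dropout stated as 12 participants, 72 randomised.

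- Plan's figure: 60 × 0.20 = 12 and 60 + 12 = 72, as stated.
- Share of those randomised: 12 / 72 = 16.7%.
- If 20% of the 72 were lost: 72 × 0.20 = 14.4.

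These are all-cause planning losses. Section 6.7 includes losses before any dose (for example a positive alcohol, drug or pregnancy test at Period 1 admission) and losses after both doses (for example a missed last sample in Period 2). Only a loss between the two doses leaves a participant dosed once, and only some of those would be for adverse events. The documents give no rate for this. Within the allowance of 12, the number could be anything from 0 to 12, and 12 is not a cap.

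**The case against.** The strongest defence is that safety belongs to the clinical report, not the statistical chapter. In a bioequivalence trial whose objective (Section 4) does not mention safety, the entry in 13.6 can be read as meaning no inferential safety analysis. Section 10 re-evaluates everyone dosed at least once, classifies each event, and enters it in the Clinical Report. The synopsis promises analysis by severity and causality, not rates by formulation.

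Much of this stands, and it rules out four stronger readings that a reader might infer:

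- **That events in withdrawn participants are lost.** They are not; Section 10.2.2 and the text after it expressly cover them.
- **That the plan produces a safety summary biased by restriction to completers.** No such summary is planned, and the completer sentence most likely concerns pharmacokinetics.
- **That the trial could not show whether events cluster on one formulation.** The forms and dosing records would allow it; what is missing is the instruction.
- **That 16.7% of participants would be dosed once, withdrawn for an adverse event and left out.** The 12 of 72 is an allowance for losses from any cause at any time.

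The defence does not remove the contradiction. Classifying and listing individual events is not analysing them, and no section states a count, a denominator or a table. If 13.6 was meant to exclude only inferential testing, it should say so and point to the descriptive output.

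**Conclusion.** The point holds as a defect in the analysis plan, not in safety collection, follow-up or reporting. Section 13.6 contradicts the synopsis; no all-dosed analysis set exists; and the only population rule is not limited to the analysis it was probably written for. Following the plan as written produces no event frequencies by formulation over participants dosed.

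The number of participants affected cannot be estimated from the documents. The figure of 12 of 72 (16.7%) is only the planned all-cause loss. The conclusion does not depend on it, because the missing tabulation affects completers' events as well.

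The bioequivalence conclusion is untouched. The change should be made because it determines what the trial can report on tolerability, at very little cost. The reading of the completer rule as intended for pharmacokinetics is an inference from its position in Section 13, which the sponsor should confirm.

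**What to change.** 1. **Replace Section 13.6** with a descriptive safety analysis, without hypothesis tests, of every participant who received at least one dose. For each formulation, give participants with at least one event over participants dosed with that formulation, by intensity and by causality. Use the period and treatment code on RQ-017 and RQ-018 together with the dosing records.
2. **State the attribution rule.** A workable choice is the formulation most recently taken at onset, so that events in the washout count towards the Period 1 formulation. Registration begins at consent, so list events before the first dose separately.
3. **Summarise pre-study and post-study ECG, laboratory and thyroid results overall only**, from the case report form and not from the event forms, because for completers the change spans both formulations.
4. **Add to Section 13** that the rule on completing both periods applies only to the pharmacokinetic and bioequivalence analysis.
5. **Align the synopsis data analysis plan** with the new Section 13.6.

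The cost is protocol wording and a few descriptive tables from data already planned. No participants, visits or procedures are added; sample size, power and the bioequivalence decision stay as they are.
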